10.2 SECONDARY ANALYSIS

10.2.1 Superiority Test of Bim SR 10 µg versus SLT

As the secondary efficacy analysis, a superiority test of Bim SR 10 µg versus SLT will be performed if the statistical noninferiority is demonstrated in the primary efficacy analysis for the ITT population as the gatekeeping procedure to control overall type I error rate at the 0.05 level. Superiority of Bim SR 10 µg versus SLT is considered achieved if the upper limit of the 95% CI is < 0 mmHg at Weeks 4, 12, and 24.

10.2.2 Time to Initial Use of Non-study IOP-lowering Treatment

Time to the initial use of non-study IOP-lowering treatment from the Date of the First Treatment as defined below will be analyzed using Kaplan-Meier (KM) method with graphical displays:

- Time to initial use of non-study IOP-lowering treatment = (Date of initial use of non-study IOP-lowering treatment – Date of the First Treatment) +1,

where the Date of the First Treatment for SLT is the SLT Treatment date (Day 1), and the Date of First Treatment for Bim SR 10 µg is Bim SR 10 µg administration date (Day 4).

Additionally, for Bim SR 10 µg, the time to non-study IOP-lowering treatment from the second injection will be summarized:

- Time to initial use of non-study IOP-lowering treatment from the second Bim SR 10 µg administration = (Date of initial use of non-study IOP-lowering treatment after the second Bim SR 10 µg implant – Date of the second Bim SR 10 µg administration) +1

In the calculation of time to initial use of non-study IOP-lowering treatment, if a patient did not use any non-study IOP-lowering treatment in an eye, then the event (initial use of non-study IOP-lowering treatment) time will be censored at the study exit date or the last visit date if the study exit date is not available.

In the calculation for the time to the event of non-study IOP-lowering treatment from the second Bim SR 10 µg administration, patients with at least two Bim SR 10 µg administrations will be used, and the event will be censored at the last available visit date or exit date if the patients did not use any non-study IOP-lowering treatment.

10.2.3 Percentage of Bim SR and SLT Eyes Achieving ≥ 20% Reduction by Visit

Number and percent of eyes that have achieved a ≥ 20% reduction in IOP at each post-baseline visit will be summarized by treatment.

10.2.4 IOP Changes from Baseline at Weeks 8, 15, and 20

IOP values at Week 8, 15 and 20 and the changes from baseline will be descriptively summarized for Bim SR 10 µg and SLT at each timepoint for the ITT population.

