 - b. Peripheral anterior chamber depth by Van Herick examination $\geq 1/2$ corneal thickness

- Note: The independent eligibility assessments must both agree that the Shaffer grade is ≥ 3 and the Van Herick grade is $\geq 1/2$ corneal thickness
13. At the Baseline visit, patient has been appropriately washed out of all IOP-lowering medications
 14. At the Baseline visit (8:00 am \pm 1 hour), IOP of ≥ 22 and ≤ 34 mm Hg, with difference between eyes of ≤ 5 mm Hg
 15. At the Screening and Baseline (Day -3 to -1) visits, Best-Corrected Visual Acuity (Snellen equivalent, by manifest refraction) of 20/50 or better in each eye

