4.5.2 Prohibited Medications/Treatments

The decision to administer a prohibited medication/treatment is taken with the safety of the study participant as the primary consideration. When possible, Allergan should be notified before the prohibited medication/treatment is administered.

During the study, patients must not participate in other investigational drug or device studies.

Nonstudy IOP-lowering Treatments

Any concurrent nonstudy IOP-lowering treatment (eg, topical ophthalmic medication containing an ocular antihypertensive, LT) is prohibited in either eye during the study (through Month 24), unless necessary for the safety of the patient due to inadequate control of IOP as determined by the investigator. Inadequate control of IOP should be confirmed at a subsequent visit (scheduled or unscheduled visit). Initiation of treatment in one eye should not automatically lead to initiation of treatment in the contralateral eye. Each eye should be evaluated on an individual basis when determining the need for additional nonstudy IOP-lowering treatments. If nonstudy IOP-lowering treatment is initiated, the investigator will be expected to attest to the need for additional nonstudy IOP-lowering treatment for safety reasons for each eye individually. Use of any concurrent nonstudy IOP-lowering treatment with any known effect on study outcomes (eg, crossover effect on the contralateral eye) is prohibited during the study.

In order to maintain patient masking to treatments assigned to each eye, patients who have received nonstudy topical IOP-lowering treatment in a Bimatoprost SR eye will receive Sham Bimatoprost SR administration in that eye on the Bimatoprost SR Cycle 2 administration day(s). If nonstudy topical IOP-lowering medication is initiated in an SLT eye, the patient will continue to receive Sham Bimatoprost SR administration in the SLT eye on the administration day(s). In all cases, the contralateral eye that does not require nonstudy topical IOP-lowering medication will maintain the same treatment regimen assigned at randomization. Patients who have received nonstudy IOP-lowering treatment in both eyes will not receive Bimatoprost SR administration or Sham Bimatoprost SR administration in either eye, and therefore do not need to attend the Bimatoprost SR (or Sham Bimatoprost SR) administration visits and immediate postadministration visits (ie, Bimatoprost SR Cycle 2

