7.3.2 Secondary Efficacy Analyses

Secondary efficacy analyses will be performed for patients treated with Bimatoprost SR 10 µg in the ITT populations.

Superiority Test of Bimatoprost SR 10 µg Versus SLT

A superiority test of Bimatoprost SR 10 µg versus SLT will be performed once noninferiority is demonstrated in the primary efficacy analysis. Superiority of Bimatoprost SR 10 µg versus SLT is considered achieved if the upper limit of the 95% CI is < 0 mm Hg at Weeks 4, 12, and 24.

Time to Initial Use of Nonstudy IOP-lowering Treatment (As Determined by the Investigator)

Time to initial use of nonstudy IOP-lowering treatment from the date of the first study treatment will be estimated separately for Bimatoprost SR 10 µg and SLT .

Additionally, time to initial use of nonstudy IOP-lowering treatment from the second injection, will be analyzed similarly for Bimatoprost SR 10 µg.

Percentage of Bimatoprost SR and SLT Eyes Achieving $\geq 20\%$ Reduction in IOP

Number and percent of Bimatoprost SR 10 µg and SLT eyes that have achieved a $\geq 20\%$ reduction in IOP by visit in each eye will be summarized.

IOP Change from Baseline at Weeks 8, 15, and 20

Summary statistics for Bimatoprost SR 10 µg and SLT eyes will be tabulated for IOP change from baseline at Weeks 8, 15 and 20; [REDACTED]

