6.1 INTENT-TO-TREAT POPULATION

Patients whose primary eyes were randomized to receive either Bim SR or SLT treatment will be referred to as randomized patients. The intent-to-treat (ITT) population is defined as all randomized patients and will be referred to as the “ITT population”. Analyses using the ITT population will be based on the randomized treatment assigned to each eye.

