10.0 EFFICACY ASSESSMENTS

The primary efficacy measurement is IOP at Hour 0, which will be measured in each eye using the Goldmann applanation tonometer. Two consecutive measurements will be taken for each eye. If the first 2 measurements differ by > 1 mm Hg, a third measurement will be taken. The IOP value for a given eye will be the median of all measurements, and this is consistent with the protocol IOP description in Study Protocol Section 6.1.1 (If the first 2 measurements differ by ≤ 1 mm Hg, the IOP for the given eye will be the average of the 2 readings. If the difference between the first 2 measurements is > 1 mm Hg, the IOP for the given eye will be the median of the 3 readings). For consenting patients at selected sites, additional IOP data will be collected at Hour 2 and 8, and these data will be included in diurnal IOP analyses.

Unless specified otherwise, the IOP measurements obtained after initiating the use of non-study IOP-lowering treatment (medications or procedures or both) in an eye will be excluded from the efficacy analysis.

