- Time to onset of effect = $(\text{Date of the earliest observation of } \geq 20\% \text{ reduction} - \text{Date of First Treatment}) + 1$

where the Date of First Treatment for SLT is SLT treatment date (Day 1), and the Date of First Treatment for Bim SR 10 μg is the first administration date (Day 4).

For eyes that did not achieve $\geq 20\%$ reduction in IOP at any post-baseline visit, 'Time to onset of effect' will be censored at the date of the latest IOP measurement. Due to large IOP drop on the day immediately after treatment, the IOP values within two days after SLT or Bim SR 10 μg treatment will not be considered for this analysis. Time to onset of effect associated with each eye will be analyzed using Kaplan-Meier method with graphical displays.

10.3.3 Percentage of Bim SR and SLT Eyes Achieving $\geq 15\%$ and $\geq 30\%$ Reductions in IOP by Visit

Number and percent of eyes that have achieved a $\geq 15\%$ reduction in IOP will be summarized by visit and by treatment. Similar summaries for patients achieved $\geq 30\%$ reductions in IOP will be provided.

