17.0 DATA HANDLING CONVENTIONS

17.1 EFFICACY DATA

As stated in protocol Section 4.5.2 Prohibited Medications/Treatments, eye(s) may receive non-study IOP lowering medication or procedure. To avoid confounding of efficacy data, IOP measurements obtained after initiating the use of non-study IOP-lowering medication or procedure in an eye will be treated as missing for that eye unless specified otherwise.

For sensitivity analyses, missing data will be imputed using the last observation carried forward (LOCF) and multiple imputation method as detailed in Section 17.2.

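### The by-visit responder tables set no rule for rescued eyes; under the SAP's default these eyes drop out, which can flatter the treatment with more rescue

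*SAP*

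**What the plan says.** The percentage of eyes reaching a 20% reduction is a named secondary variable (Protocol 7.2.2). SAP 10.2.3 gives it one sentence: the number and percent of eyes with that "reduction in IOP at each post-baseline visit will be summarized by treatment". SAP 10.3.3 treats 15% in the same way ("reduction in IOP will be summarized by visit and by treatment") and promises a similar summary for 30%, where the unit changes from eyes to patients. Protocol 7.3.2 adds no detail. None of these sections states a per-visit denominator or how a rescued eye is classified.

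The general data rule is stated. SAP 10.0 says that, absent other instruction, "the IOP measurements obtained after initiating the use of non-study IOP-lowering treatment (medications or procedures or both) in an eye will be excluded" when efficacy is analysed. SAP 17.1 says that such readings "in an eye will be treated as missing for that eye unless specified otherwise". The SAP's only formula for percentage reduction (10.3.2) is applied to whichever post-baseline IOP visits an eye has available.

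Protocol 4.5.2 prohibits non-study IOP-lowering treatment "unless necessary for the safety of the patient due to inadequate control of IOP as determined by the investigator", and requires the decision to be made for each eye separately.

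**The concern.** The responder sections specify nothing else, so the default leads to an observed-case table: once an eye is rescued, it has no usable value and most likely leaves both numerator and denominator at later visits. It leaves because its pressure was judged inadequately controlled, so the loss is informative, and it accumulates over visits running to Month 24. Unequal rescue is plausible, because SLT is given once while the Bimatoprost SR eye may receive a second implant (Protocol 5.6). The documents do not show which treatment will have more rescue.

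The planned missing-data methods do not reach these tables. LOCF (SAP 10.4.2, 17.2.1), multiple imputation (17.2.2), the tipping-point analysis (10.4.4) and the analysis regardless of rescue (10.4.3) all concern IOP change. Number and percent together let a reader recover the denominator, but not whether an absent eye was rescued, had left the study or missed a visit.

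**Working it through.** The plan states no figure for these tables. It does supply a scale: 144 evaluable patients and 10% discontinuation (Protocol 7.5, SAP 15.0), which reproduce as 144/(1 − 0.10) = 160 enrolled. Each patient contributes one eye per treatment.

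**Assumed, because the documents give no rates:**
- N = 144 eyes per treatment, with no other missing data.
- S = 80 eyes per treatment (80/144 = 55.6%) would reach 20% without rescue, so the true gap is 0.
- r eyes are rescued before the visit: 14 in treatment A (about 10%) and 43 in treatment B (about 30%).
- q is the share of rescued eyes that would still have met 20%. Rescue is not the same as missing 20%: the baseline range reaches 34 mm Hg (Protocol 4.3, criterion 14), and a fall from 34 to 27 is 7/34 = 20.6%.

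**Formulas:** observed-case = (S − q·r)/(N − r); rescued eyes kept as non-responders = (S − q·r)/N.

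| q | Observed-case A | Observed-case B | Gap, B − A | Kept as non-responders A | Kept as non-responders B | Gap, B − A |
|---|---|---|---|---|---|---|
| 0 | 80/130 = 61.5% | 80/101 = 79.2% | +17.7 | 55.6% | 55.6% | 0 |
| 0.25 | 76.5/130 = 58.8% | 69.25/101 = 68.6% | +9.7 | 53.1% | 48.1% | −5.0 |
| 0.5 | 73/130 = 56.2% | 58.5/101 = 57.9% | +1.8 | 50.7% | 40.6% | −10.1 |
| 0.75 | 69.5/130 = 53.5% | 47.75/101 = 47.3% | −6.2 | 69.5/144 = 48.3% | 47.75/144 = 33.2% | −15.1 |

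The observed-case gap is zero at q = S/N = 80/144 = 0.556 and changes sign above it. For q from 0 to 0.556 the true gap of 0 lies between the two versions. Above 0.556 both err against the treatment with more rescue.

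**Smaller contrast:** 7 versus 14 rescued (about 5% versus 10%), q = 0: 80/137 = 58.4% versus 80/130 = 61.5%, a gap of 3.1 points.

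**Reversal:** 160 eyes per treatment, true response 80 versus 72 (50% versus 45%), 16 versus 48 rescued, q = 0. Observed-case gives 80/144 = 55.6% versus 72/112 = 64.3%, so the order is reversed.

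**Exits:** suppose 16 of 160 patients leave and each had one rescued eye, all of the same treatment. If the rescued eye stays in the table while its fellow eye is dropped, equal response reads 80/160 = 50.0% versus 80/144 = 55.6%. If both eyes are dropped, 16 known rescues vanish. Over all 160 eyes per treatment it reads 50.0% for both, and the rescues remain counted.

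**The case against.** The strongest reply is that treating post-rescue IOP as missing is a deliberate choice, in line with the hypothetical strategy declared for the primary analysis (SAP 10.1), so counting rescue as failure is simply another estimand. That stands in part, and it is a reason to keep the observed-case table. But the MMRM uses an eye's other visits and its fellow eye to handle the missing value; a raw percentage just drops the eye.

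A second reply is that the ITT population already settles the denominator: "Secondary efficacy analyses will be performed for patients treated with Bimatoprost SR 10 µg in the ITT populations", and "Analyses using the ITT population will be based on the randomized treatment assigned to each eye". Those sentences fix who is analysed and under which treatment. They do not say that an eye without a usable reading is a non-responder, and the default together with 10.3.2 points to observed-case.

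Third, the consequences are limited. No test or alpha attaches to these tables. Rescue is reported by Kaplan-Meier (10.2.2) and by eye in the medication tables (8.4.2), and discontinuations are tabulated with reasons (7.0). All of this stands, although none of it separates rescue from other absence within a visit's responder table.

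Fourth, the 17.7-point figure needs a threefold difference in rescue and q = 0. That is also fair: it is the top of an assumed range, not a forecast.

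A reader might infer more: that the noninferiority result is compromised, or that the table will favour a particular treatment. The documents support neither. These tables play no part in the noninferiority or superiority decision, and the direction depends on unknown rescue rates and on q. Nor does the concern extend to the time-weighted average in 10.3.1, whose rule for missing visits is explicit. The only gap there is that the text does not say whether baseline enters the post-baseline IOP average.

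**Conclusion.** The point holds for the responder tables in SAP 10.2.3 and 10.3.3. No rule is set for rescued eyes, the default most likely removes them, and the percentage is then inflated for the treatment with more rescue if rescued eyes are mostly non-responders. With equal true response, the illustrated spurious gap runs from about 3 to 18 points at q = 0; in the 10% versus 30% case it disappears at q = 0.556 and reverses beyond that. These sizes rest on assumed response and rescue rates. It affects how a named secondary variable reads and leaves the primary conclusion untouched. It should be settled before unmasked results are seen, so that the choice of denominator is not open afterwards.

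**What to change.** In SAP 10.2.3 and 10.3.3:

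- Keep the observed-case table and print its n at each visit.
- Add beside it a version whose denominator is all ITT 10 µg eyes, both eyes of every patient, so that the treatments share one denominator. An eye is a non-responder at every analysis visit after its first non-study IOP-lowering treatment, including after the patient exits. Eyes missing for other reasons also count as non-responders. Visits not yet due at a given lock should not be tabulated as failures.
- Show by visit and treatment the number rescued and the number missing for other reasons.
- Use the same analysis windows for both versions, and say which part of Table 17-2 applies.
- Use eyes as the unit at all three thresholds.

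In 10.3.1, at most add that baseline is left out of the post-baseline IOP average.

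The cost is some SAP text and programming for a second version at three thresholds; no visit, data collection or clinical rule changes. Percentages at later visits will be lower. Rescue decisions enter the second version, and the primary investigator is unmasked (Protocol 9.4). Some rescued eyes that would have met the threshold count as failures, so this version can understate the treatment with more rescue. That is why the observed-case table and the counts stay beside it.

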10.3 OTHER EFFICACY ANALYSES

Other efficacy analyses comparing Bim SR 10 µg and SLT include:

- IOP change from baseline as time-weighted average through Week 24
- Post-baseline IOP as time-weighted average through Week 24
- Time to first achieving ≥ 20% IOP reduction
- Percentage of eyes achieving ≥ 15% and ≥ 30% reductions from baseline IOP by visit
- Diurnal IOP

Analyses will be performed for the ITT population. KM method will be used for time to event analysis.

For patients treated with Bim SR 15 µg, descriptive statistics for baseline and change from baseline IOP will be summarized for each eye (SLT and Bim SR 15 µg) and visits in the ITT population.

10.3.1 IOP Change from Baseline (and Post-baseline IOP) Time-weighted Average through Week 24

Time-weighted average change in IOP from baseline is calculated as described below:

Let y_0, y_1, \dots, y_n represent IOP measurements taken on calendar dates d_0, d_1, \dots, d_n respectively, where y_0 is the measurement taken on calendar date d_0 , representing baseline IOP value, and let $\Delta y_i = y_i - y_0$, representing the change in IOP from baseline to date d_i for $i=0, 1, \dots, n$. Then the time-weighted average change, denoted by S_1 is:

$$S1 = \frac{1}{(d_n - d_0)} \sum_{k=1}^n (\Delta y_k + \Delta y_{k-1}) \times \frac{(d_k - d_{k-1})}{2}$$

In this analysis, IOP measurements taken at Baseline (at d_0), Week 4, Week 8, Week 12, Week 15, Week 20, and Week 24 will be considered, thus $n = 6$. The analysis visit with missing value will be skipped from the calculation. S1 will be calculated for each patient and each eye by using the actual dates of the IOP measurements. The time-weighted average change from baseline will be summarized descriptively by Bim SR 10 μg eye and SLT eye. Similar equation will be applied for the time-weighted average post-baseline IOP.

10.3.2 Time to Onset of Effect (Time to First Achieving $\geq 20\%$ IOP Reduction)

Percentage reduction in Hour 0 IOP from baseline will be calculated for all available post-baseline IOP measurement visits for each eye using the formula:

- Percentage Reduction = $100 \times (\text{Baseline IOP} - \text{Visit IOP}) / \text{Baseline IOP}$

Time in days to onset of effect will be calculated using the Date of First Treatment and the date of the earliest observation of $\geq 20\%$ reduction in IOP using the formula:

- Time to onset of effect = $(\text{Date of the earliest observation of } \geq 20\% \text{ reduction} - \text{Date of First Treatment}) + 1$

where the Date of First Treatment for SLT is SLT treatment date (Day 1), and the Date of First Treatment for Bim SR 10 μg is the first administration date (Day 4).

For eyes that did not achieve $\geq 20\%$ reduction in IOP at any post-baseline visit, 'Time to onset of effect' will be censored at the date of the latest IOP measurement. Due to large IOP drop on the day immediately after treatment, the IOP values within two days after SLT or Bim SR 10 μg treatment will not be considered for this analysis. Time to onset of effect associated with each eye will be analyzed using Kaplan-Meier method with graphical displays.

10.3.3 Percentage of Bim SR and SLT Eyes Achieving $\geq 15\%$ and $\geq 30\%$ Reductions in IOP by Visit

Number and percent of eyes that have achieved a $\geq 15\%$ reduction in IOP will be summarized by visit and by treatment. Similar summaries for patients achieved $\geq 30\%$ reductions in IOP will be provided.

10.3.4 Diurnal IOP Analyses

For consenting patients at selected sites, diurnal IOP measurements will be conducted at Hour 0, 2, and 8. The diurnal IOP measurements will be summarized by hour and by visit. Additionally, descriptive statistics for the mean IOP across Hours 0, 2, and 8 will be summarized by visit for patients who had least 2 IOP measurements available out of 3 timepoints. Similarly, descriptive statistics of the IOP range (max IOP – min IOP among three timepoints) will be summarized by visit.

10.3.5 Baseline Hour 0 IOP and Change from Baseline in Bim SR 15 µg

For patients treated with Bim SR 15 µg, descriptive statistics for baseline and change from baseline in Hour 0 IOP will be summarized for Bim SR 15 µg and SLT separately at each visit.

10.4 SENSITIVITY ANALYSES

10.4.1 Per Protocol Analysis

As part of the sensitivity analyses, the mean difference and 95% CI in the IOP change from baseline between the Bim SR 10 µg and SLT (Bim SR 10 µg minus SLT) will be constructed for Week 4, 12, and 24 visits for the Per Protocol (PP) population using the same MMRM model as specified for the primary analysis.

10.4.2 Analysis of Covariance (ANCOVA)

Analysis of Covariance (ANCOVA) including within-patient correlation at each visit will be conducted for IOP change from baseline at Weeks 4, 12, and 24 in the ITT population. In this analysis, missing data will be imputed using the last observation carried forward. At each visit, the model for IOP change from baseline is specified as: IOP Change from Baseline = Treatment + Eye + Baseline IOP, where Eye is a primary eye or a contralateral eye. Unstructured covariance matrix will be used for between eye correlation.

